The type (i.e., the international nonproprietary name, the dose, and the projected last dose of all antiplatelet agents) must be predeclared at randomization. ASA 75-100 mg/day or generic/branded clopidogrel 75 mg/day (chronic therapy following loading dose) are the preferred agents. Type, dose, and (projected) last dose may be changed during the treatment period for documented medical reasons.

Study Duration:

Subjects will be monitored throughout the entire study period regardless of whether they have or have not experienced an endpoint. Monitoring will be performed with study visits (which can be on-site or at the subject's current place of living, but the monitoring will be conducted by the Investigator or qualified designee) at 3 and 6 months post randomization, then semi-annually, at the end of the treatment period, and at 30 days after the last dose of the study medication (see [Table 17.1](#)). After the End of Treatment Visit, subjects will have the option to be followed by telephone contact with the site and/or review of their

medical records by qualified site personnel until the end of the study (common study end date [CSED]).

The enrollment will be stopped no later than at the attainment of a total of 320 subjects experiencing an adjudicated NACE across the combined treatment arms, and the study will continue until the last subjects enrolled will have accomplished the minimum treatment duration of at least 6 months plus their Post-treatment Follow-up Visit.

Study Sites and Locations: It is planned to enroll approximately 1400 subjects with a 1:1 randomization ratio (Edoxaban: VKA) approximately 200 study sites located in the USA, Canada, Europe (Austria, Belgium, France, Germany, Italy, the Netherlands, Spain, Switzerland, UK and potentially other countries), and Japan. Other countries may also participate.

Planned Sample Size: The primary endpoint is NACE.

In order to determine the sample size, the following assumptions were made:

- *Event rate:* Based on published literature and results from the ENGAGE AF-TIMI 48 study, it is assumed that the event rate of the primary efficacy endpoint of NACE in AF-subjects treated post TAVI with VKA would be 14%/year.

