5.8. Subject Withdrawal/Discontinuation

The intended duration of the two treatment regimens is up to 36 months. Subjects must stay on the assigned OAC-based regimen as much as possible.

Discontinuation of the assigned regimen is mandatory if the CrCL falls below 15 mL/min on two consecutive occasions or if subject is placed on dialysis. If the Investigator doubts the accuracy of the CrCL value calculated with the Cockcroft-Gault formula (Section 17.7), he/she may consider calculating CrCL using a 24-hour urine collection, for confirmatory purposes. If a subject's CrCL, calculated with either the Cockcroft-Gault formula or 24-hour urine collection, recovers to > 15 mL/min, the subject should resume study regimen in line with the applicable labels.

For subjects with a suspected transient decrease in CrCL < 15 mL/min it is recommended that repeat testing of CrCL occur after corrective action is taken or when the medical condition that caused the worsening renal function resolves. The timing of the repeat testing is at the discretion of the Investigator and will vary depending on the nature of the medical condition (e.g., 1-2 weeks for urinary tract infection or over diuresis vs. several weeks to months for glomerulonephritis).

If other clinical contraindications for any study medication develop (according to the label of the respective drug), the study medication must be discontinued (or dose decreased if applicable). If the contraindication resolves, the respective study medication is restarted. During each interruption of anticoagulant or antiplatelet therapy, subjects are evaluated to determine whether the subject can safely resume the study drug. A post-randomization change in health status that results in the subject meeting one or more of the exclusion criteria should only lead to interruption or discontinuation of the assigned medications if the change in health status implies a contraindication according to the drug labels.

Study medications are permanently discontinued if the subject refuses continuation of any medication in the assigned study regimens.

All subjects are followed through to the termination of the study irrespective of changes in the antithrombotic regimen. Clinical follow-up before the end of the study is only terminated at the explicit documented request of the subject or his/her death.

All study drug start and stop dates are captured in eCRF together with the reason for interruption or discontinuation.

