5.8.2. Subjects with Study Drug Interruptions/Discontinuations

The Investigator should call the CRO medical monitor in case of any questions regarding how to handle a study medication interruption and/or discontinuation.

Suspension/Interruption: The date/time of the last dose, the reason for the interruption, and other required details will be recorded in the eCRF. Reasons for interruption include but are not limited to: development of clinical contraindications for any study drug (according to the label of the respective drug). During each interruption of anticoagulant or antiplatelet therapy, subjects are evaluated to determine whether the subject can safely resume the study drug.

Discontinuation: The date/time of the last dose, the reason for the discontinuation, and other required details will be recorded in the eCRF. For some potential reasons for discontinuation of study drug see Section 5.8.1 and locally approved drug label.

During a study drug interruption or after study drug discontinuation, a subject can be placed on another antithrombotic therapy per local guidelines and Investigator discretion. All randomized subjects, including those who discontinued study medication, will be followed through the overall end of the study for the primary and secondary efficacy and safety endpoints and SAEs. If the subject has an onsite visit, it is expected that vital signs will be obtained along with any laboratory assessments deemed appropriate by the Investigator.

If a subject who discontinues study drug also withdraws consent, in writing, for participation in the study, the protocol-specified consent withdrawal procedures (Section 5.8.3) must be completed.

If the subject interrupts (or discontinues) study drug due to an AE, the Investigator will follow the event until it has resolved or stabilized.

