- Draw blood for analysis by an accredited/certified local laboratory (Section 9.9) (if recent [within the 15 days before randomization] are available from standard of care, these values may be used instead of requiring an additional blood draw). Creatinine and CBC must be available from blood draws after TAVI and the subject must be clinically stable. CrCL should be calculated by the Cockcroft-Gault formula as described in Section 17.7 and the results need to be available prior to the 1st dose of study drugs for subjects randomized to Edoxaban. Include a liver panel only if recent (within the 15 days before randomization) results are not already available.
- For childbearing potential female subjects, a urine pregnancy test (e.g., dipstick test) will be performed at Randomization, 3 months, 12 months, 24 months, and End of Treatment Visits. Furthermore, pregnancy tests will be carried out whenever there are clinical indications for the existence of a pregnancy.
- First administration of assigned study medication **within 24 hours of randomization**; however, **NO EARLIER** than the morning after successful TAVI.
- Record date/time of first study medication administration in eCRF
- Instruct subject on the use of study medication (see Section 3.1)
- Instruct subject on the use of the memory aid
- Dispense assigned OAC

- Daiichi Sankyo supplies study subjects with Edoxaban. VKA and OAP may be supplied by the site or via prescriptions issued either by the site or attending physician. See Section 3.1 about OAP administration.
- Assessment and recording of (S)AEs and suspected clinical events will start immediately after signed informed consent and continue until 30 days after the end of treatment with study medication.

The randomized treatment strategy is implemented after randomization without any undue delay.

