- Confirm consent to participate in Post Discontinuation/Follow-up Contact;

Transition subject to appropriate medication (Section 5.2.1)**Note: In subjects with early permanent discontinuation of the assigned therapy every attempt made to have the Follow-up Visit performed.**

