6.7. Post Discontinuation/Follow-up Contact

- Subjects (unless they refuse to participate) will be called approximately every 6 months (\pm 1 month) until the Sponsor determines the end of the study to assess the subject's vital status, occurrence of potential endpoint events, or any SAEs. This information may be obtained from relatives, public records, or the treating physician. Should the subject choose to not receive phone calls, the site may attempt to retrieve this information from viewing the subject's medical records or public records.

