- k Assessment and recording of (S)AEs and suspected clinical events from the signing of the informed consent, and should be reported as soon as site personnel learn of the event and be reported within 24h of the Investigator's/site's awareness. Endpoint event and AE reporting should occur throughout the study and not be restricted to specific visits. If AST or ALT $> 3 \times \text{ULN}$ with simultaneous total bilirubin levels $> 2 \times \text{ULN}$ is observed, then ALP should be determined. Hospitalization due to cardiovascular events needs to be assessed.
- l When subjects are being transitioned to non-study medications, record the date and time of last administration of study medication, and collect all unused study medication. Subjects are transitioned to an approved OAC of the Investigator's or treating physician's choice. The Investigator will follow the transition strategy in the approved product label. Subjects who prematurely discontinue study OAC are requested to also complete the Post-treatment Follow-up Visit according to this schedule (See Section 5.2.1.1.2 and Section 5.2.1.2.2).

m EOT may occur at any time (e.g., at subject withdrawal or discontinuation) and will trigger this subject's Post-treatment Follow-up Visit.

n Female subject who are of child bearing potential.

o Female subject who are of child bearing potential. Furthermore, pregnancy tests are carried out whenever there are clinical indications for the existence of a pregnancy.

p All subjects who have taken study medication should be requested to consent for routine follow-up contact at 6-month intervals following termination of study drug. This will normally be as a phone contact until the end of the study is determined by the Sponsor. Should the subject choose to not receive phone calls, the site may attempt to retrieve this information from viewing the subject's medical records or public records.

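### Endpoint follow-up to study end is required for all randomized subjects, but Section 6.2, footnote p and the optional wording are narrower, so events after stopping drug may go uncollected

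*Combined protocol and SAP*

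**What the plan says.** **The general rule.** Protocol Section 5.8.2 states: "All randomized subjects, including those who discontinued study medication, will be followed through the overall end of the study", for primary and secondary endpoints and SAEs. Section 5.8 adds: "Clinical follow-up before the end of the study is only terminated at the explicit documented request of the subject or his/her death".

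**Text that supports the rule.**
- Section 6.7: "Subjects (unless they refuse to participate) will be called approximately every 6 months" until study end, for vital status, endpoint events and SAEs. Medical or public records are the fallback.
- Section 9.1: six-monthly collection, including endpoint events, after permanent discontinuation.
- Section 9.5.1: AEs and SAEs are reported for as long as the subject remains in the study.
- Table 17.1: the row for suspected clinical events is ticked at the follow-up contact (Visit 10). Footnote k says endpoint reporting runs throughout the study.

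**Text that is narrower.**
- Section 6.2: recording of AEs, SAEs and "suspected clinical events will start immediately after signed informed consent and continue until 30 days after the end of treatment with study medication".
- Table 17.1, footnote p: "All subjects who have taken study medication should be requested to consent for routine follow-up contact at 6-month intervals following termination of study drug".
- Synopsis, Study Duration: "After the End of Treatment Visit, subjects will have the option to be followed by telephone contact with the site", with record review as an addition or alternative.
- Sections 6.5 and 6.6: "Confirm consent to participate in Post Discontinuation/Follow-up Contact".

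**How the data are used.** All four primary hypotheses are tested in the ITT set, which includes never-dosed subjects (Sections 11.1.1 and 11.4.1). Nothing is imputed, and incomplete subjects are censored at last known status (Section 11.2).

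**The concern.** A site has two sets of instructions for the same task. Section 6.2 sits in the procedures chapter and footnote p in the visit schedule, which are the places site staff consult. A coordinator who follows them could properly stop recording endpoint events 30 days after the last dose, and could find no follow-up contact described for a subject who was randomized but never dosed. The 30-day visit in Section 6.6 is also timed from last study treatment, which such a subject does not have.

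The stakes lie in the ITT comparison. Treatment is open-label, and Section 5.8.1 lists AEs, major life-threatening bleeding and reaching a primary endpoint among the reasons for interrupting or stopping study drug. Subjects who stop may therefore differ in risk from those who continue, and stopping may differ by arm. If their later events are not collected, the Cox model censors them as if censoring were unrelated to risk. In a noninferiority comparison, a bias towards no difference makes the noninferiority claim easier when the test arm is the one losing events. Events not collected during follow-up may not be recoverable at analysis.

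**Working it through.** **1. The passages side by side**

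| Question | Sections 5.8 and 5.8.2 | Narrower text |
|---|---|---|
| Until when are endpoint events recorded? | End of study | 30 days after end of treatment (6.2) |
| For whom? | All randomized | Those who took study medication (footnote p) |
| What ends follow-up? | Documented request, or death | Not agreeing to contact (footnote p; a possible reading of the synopsis, 6.5 and 6.6) |

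The first row is a direct contradiction. The second is a restriction by implication, because footnote p does not say that never-dosed subjects are not followed. The third depends on how the wording is read.

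**2. Illustration of the 30-day stop**

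Inputs from Section 11.9: 1400 subjects, NACE rate λ = 0.14 per year, follow-up T = 2 years (the stated median, applied here to everyone). From Section 6.2: L = 30/365.25 = 0.0821 years. Assumed, because the documents give no figure: exponential discontinuation at c = 0.10 or 0.20 per year.

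*Full follow-up:* 1 − e^(−0.14×2) = 0.24422, and 1400 × 0.24422 = 342 first events. This is the same order as the planned 320. (The 320 target itself does not follow from the stated inputs: 4(1.960 + 0.842)²/[ln(1.38/0.95)]² gives 226. That is a separate matter with no bearing here.)

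*With the 30-day stop, hazard unchanged after stopping:*

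captured = 1 − e^(−λL) + e^(−λL) × λ/(λ+c) × [1 − e^(−(λ+c)(T−L))]

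- c = 0.10: 0.0114 + 0.9886 × 0.5833 × 0.3689 = 0.22416, or 314 events. Missed: 1 − 0.22416/0.24422 = 8.21%.
- c = 0.20: 0.0114 + 0.9886 × 0.4118 × 0.4790 = 0.20643, or 289 events. Missed: 1 − 0.20643/0.24422 = 15.47%.

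*Sensitivity.* If the hazard doubles after stopping, the missed shares are 13.9% and 24.6%. If follow-up is instead uniform from 6 to 42 months, they are 9.4% and 17.4% (30 and 56 of 320) with unchanged hazard, and 15.4% and 26.8% (49 and 86 of 320) with doubled hazard.

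**3. Direction of bias**

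Assume an on-drug hazard of 0.14 per year in both arms, a hazard that doubles after stopping, and 2 years of follow-up. The figures are first events per subject-year.

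| Discontinuation per year, edoxaban vs VKA | Full follow-up | 30-day stop |
|---|---|---|
| 20% vs 10% | 0.1618/0.1515 = 1.07 | 0.1422/0.1411 = 1.01 |
| 10% vs 20% | 0.1515/0.1618 = 0.94 | 0.1411/0.1422 = 0.99 |

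Both move towards 1. The first case favours a noninferiority conclusion; the second works against edoxaban. If the hazard does not change on stopping, the ratio is 1.00 either way and there is no bias. The effect therefore needs both unequal stopping and a changed risk after stopping.

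**The case against.** The strongest reply is that the protocol, read as a whole, plainly intends full collection. Section 6.7 is the operational section for this follow-up, and subjects are called unless they refuse. Sections 9.1 and 9.5.1, Visit 10 in Table 17.1 and footnote k agree with it. Section 5.1.1 says follow-up may outlast treatment, Section 5.8.3 seeks endpoint follow-up even after consent is withdrawn, and Section 11.2 asks for complete follow-up regardless of discontinuation. This stands, and it rules out several stronger readings that a reader might infer:

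- *That endpoint data will be selectively missing.* The documents do not show this. They give no discontinuation or refusal rate, and most of the text provides for collection. Loss is a risk.
- *That never-dosed subjects are lost entirely.* Visits are set from randomization (synopsis) and apply to all subjects (Section 6.4), and Section 6.7 is not limited to treated subjects. First dosing is due within 24 hours of randomization and is supervised, so such subjects should be few.
- *That a subject who declines contact is lost.* Footnote p and Section 6.7 both allow record review, although only as something the site may attempt.
- *That a second consent is imposed.* Sections 6.5 and 6.6 speak of confirming consent. Only footnote p asks for it, and the consent form is not available for review. The option in the synopsis can be read as a choice of contact method.
- *That the loss reaches the primary tests whichever analysis window applies.* The primary period closes at Month 36/EOT (Visit 8), and footnote m lets EOT fall at discontinuation. If EOT is the subject's own, the 30-day stop removes nothing from the primary window, because events after discontinuation are already outside it.

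The trial is also event-driven, so a shortfall in the count could be made up by longer follow-up; bias could not. What remains is the conflict itself. Supporting passages do not cancel Section 6.2 or footnote p; they leave sites to choose between instructions.

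**Conclusion.** The inconsistency is real and should be corrected. Section 6.2 contradicts Section 5.8.2 on how long endpoint events are recorded, footnote p is narrower on whom follow-up covers, and the synopsis and Sections 6.5 and 6.6 are open to a reading in which follow-up is optional. The consequence is a possible informative loss of primary-endpoint events, of unknown size. The 8-15% of first NACE is what strict use of the 30-day stop would miss at an assumed 10-20% per year discontinuation, unchanged hazard and two years of follow-up. It is not a forecast, since many sites would follow Section 6.7. Bias in the hazard ratio further requires that stopping differ between arms and that risk change after stopping. For the primary tests, it also requires that the analysis window extend beyond the subject's own EOT. On this evidence it is a wording reconciliation worth making promptly, and not a defect that by itself undermines the primary analysis.

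**What to change.** 1. **Section 6.2.** Limit the 30-day stop to AEs that are neither serious nor suspected endpoints. State that SAEs and suspected endpoint events are recorded until the common study end date. Reconcile the AE period with Section 9.5.1, which runs to the end of participation, whereas Sections 9.1 and 9.4 use 30 days.
2. **Footnote p.** Extend it to all randomized subjects, including those never dosed, with contacts for never-dosed subjects timed from randomization.
3. **Synopsis, Sections 6.5 and 6.6, and footnote p.** State that follow-up continues unless the subject documents a request to stop, as in Section 5.8. Limit the option to the mode of contact.
4. **Section 11.2.** Settle at the same time whether Month 36/EOT (Visit 8) means the subject's own EOT or the study end. A per-subject EOT would leave events after discontinuation outside the primary analysis even if they are collected.

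**Cost.** One wording amendment, plus some additional six-monthly calls or record checks. No new type of visit or procedure is needed. The consent form needs changing only if the existing consent does not already cover this follow-up. If it does need changing, Section 15.6 brings ethics re-approval and renewed written consent, which is a real burden across about 200 sites, so that point should be checked first.

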17.1. Bleeding Criteria

17.1.1. ISTH Bleeding Criteria

Table 17.2: ISTH Bleeding Criteria²⁷

ISTH Bleeding Criteria

Major bleeding
 
 • Clinically overt bleeding that is associated with: 
 ○ A fall in hemoglobin of 2 g/dL (1.24 mmol/L) or more, or ○ A transfusion of 2 or more units of whole blood or packed red blood cells, or ○ Symptomatic bleeding in a critical site or organ such as: intracranial, intraspinal, intraocular, retroperitoneal, pericardial, intra-articular, intramuscular with compartment syndrome, or ○ A fatal outcome

Clinically relevant non-major (CRNM) bleeding
 
 • Any sign or symptom of hemorrhage (e.g., more bleeding than would be expected for a clinical circumstance, including bleeding found by imaging alone) that does not fit the criteria for the ISTH definition of major bleeding but does meet at least one of the following criteria: 
 ○ requiring medical intervention by a healthcare professional ○ leading to hospitalization or increased level of care ○ prompting a face to face (i.e., not just a telephone or electronic communication) evaluation.

Minor
 
 • Bleeding episodes not requiring any medical attention and therefore not meeting the criteria for major or clinically relevant non-major bleeding.

17.1.1.1. Definitions of terms

Abnormal liver function is defined as chronic hepatic disease (e.g., cirrhosis) or biochemical evidence of significant hepatic derangement (e.g., bilirubin > 2 X the ULN, in association with aspartate aminotransferase/alanine transferase > 3 X the upper limit of normal).

Abnormal renal function is defined as chronic dialysis, renal transplantation, or serum creatinine $\geq 200 \mu\text{mol/L}$ ($\geq 2.26 \text{ mg/dL}$).

Congestive heart failure is defined as the current presence or prior history of clinical congestive heart requiring medical attention and medical therapy or documented Ejection Fraction $\leq 35\%$ (left ventricular systolic dysfunction).

Diabetes Mellitus includes diabetes requiring treatment with diet only or with pharmacologic therapy (insulin, oral hypoglycemic agents).

Documented clinical need is defined as a known record in any form (incl. written, electronic or verbal) recording pertinent subject data with regards to the clinical reason for the choice of an alternative medication. This reason must be captured and pre-declared before subject randomization.

Labile INRs is defined as unstable or high INRs or poor time in therapeutic range (e.g., $< 60\%$) while on a Vitamin K antagonist.

Hypertension is defined as hypertension requiring pharmacologic therapy to maintain a BP $< 140/85$ mmHg or untreated hypertension documented by BP > 140 mmHg systolic or > 90 mmHg diastolic on two separate occasions.

Stroke: Stroke is defined as an abrupt onset, over minutes to hours, of a focal neurological deficit that is generally in the distribution of a single brain artery (including the retinal artery) and that is not due to an identifiable non-vascular cause (i.e., brain tumor or trauma). The deficit must either be associated with symptoms lasting more than 24 hours or result in death within 24 hours of symptom onset.

TIA: TIA is defined as an abrupt onset, over minutes to hours, of a focal non-fatal, neurological deficit in the distribution of a single brain artery (including the retinal artery) that lasts less than 24 hours and that does not satisfy the definition of stroke above.

